			Data cleaning & analysis, write-up paper/grant renewal preparation											

PROTECTION OF HUMAN SUBJECTS

E.1. Risk to the Subjects

E.1.1. Human Subjects Involvement and Characteristics

The 2-year project will enroll male and female individuals (18 and older) regular alcohol users with past month excessive use of alcohol. Research data will be collected at screening, baseline, and weekly study visits.

This study is funded by the National Institute on Alcohol and Alcoholism (NIAAA). All studies funded by NIAAA, including this study, now submit data to the National Institute of Mental Health Data Archive (NDA) at the National Institutes of Health (NIH). All subject data will be de-identified by using a computer-generated global unique identifier (GUID) within the NDA database.

The single study site is the Center for Neurobehavioral Research on Addiction (CNRA) at the University of Texas McGovern Medical School, Houston. The CNRA is centrally located in a large U.S. metropolitan area known to have an adequate and representative alcohol-using population [see Facilities and Other Resources]. Moreover, the site has demonstrated its ability to recruit and retain the appropriate population using various recruitment strategies.

We plan on recruiting 4 participants/month over the course of 20 months for a total of 80 enrolled participants. We estimate that 60 participants (75%) will complete the study, based on previous studies from our group. Recruitment strategies will include local advertising in print media, public service announcements on radio, and referrals to CNRA in the Houston metropolitan area. Additionally, we will utilize the SONA system, which provides University of Houston students credit for participating in various research studies. Potential participants will complete a brief phone screen to assess initial eligibility and subsequently invited to undergo a comprehensive baseline screening following informed consent. The baseline screening will include a full medical evaluation by the CNRA Medical Director ([name]. Co-I). All participants will meet the following selection criteria.

Inclusion criteria. Be treatment-seeking individuals diagnosed with AUD (DSM-5); be at least 18 years old and fluent in English; past month excessive alcohol use (>7 drinks/week for woman, >14 drinks/week for men, >3 drinks/occasion for women>4 drinks/occasion for men)³⁵; exhibit baseline measures of either 1) 8-23 on HAM-A indicative of mild to moderate anxiety, 2) 14-26 on PSS Score indicative of moderate stress, or 3) ≥ 2 on DMQ-R questions related to drinking indicating that individuals drink at least “some of the time” to cope; and exhibit increased stress reactivity (increased physiological response and/or self-report) at the baseline stress reactivity assessment.

Exclusion criteria. Exhibit severe scores on the HAM-A, PSS, or PTSD checklist (PCL-5) – may be enrolled at the discretion of the admitting physician ([name]); physical dependence on alcohol (CIWAA > 10); greater than mild substance use disorder on drugs other than alcohol, nicotine, and marijuana; contraindications for taking pioglitazone; medical conditions (e.g., congestive heart failure, clinically significant edema, clinically significant liver disease, hypoglycemia, diabetes, history of bladder cancer) contraindicating pioglitazone pharmacotherapy or taking contraindicated medications (e.g., CYP2C8 inhibitors or inducers, antihyperglycemic medications); be pregnant, nursing, or planning on becoming pregnant during the course of the study; females will need to agree to use of barrier methods of contraception due to pioglitazone’s effects on plasma concentrations of oral contraceptives; have any other illness, condition, or use of medications, which in the opinion of the PI and/or admitting physician would preclude safe and/or successful completion of the study.

E.1.2. Sources of Materials

We will obtain information about subjects from structured interview evaluations, physical examinations, self-report measures, biological samples, and behavioral laboratory tasks. T1   APPROVED at 01/12/2023

specified time points during the study. The biological specimens obtained from all subjects will include urine, blood, salivary cortisol, and breath samples for alcohol detection. All materials will be obtained for the specific purposes of this research.

E.1.3. Potential Risks

Medication. Pioglitazone (trade name Actos) is approved by the FDA for the treatment of type II diabetes. According to the prescribing information for Actos “Over 8500 patients with type 2 diabetes have been treated with ACTOS in randomized, double-blind, controlled clinical trials, including 2605 patients with type 2 diabetes and macrovascular disease treated with ACTOS in the PROactive clinical trial. In these trials, over 6000 patients have been treated with ACTOS for 6 months or longer, over 4500 patients have been treated with ACTOS for one year or longer, and over 3000 patients have been treated with ACTOS for at least 2 years.”

In addition, several studies have taken place in non-diabetic patients. Sixty non-diabetic patients with hypertension were treated with pioglitazone or placebo in one trial, finding a significant reduction in diastolic blood pressure in the pioglitazone treated group¹¹³.

Another larger study in non-diabetic hypertensive patients found a significant reduction in biomarkers of insulin resistance and chronic systemic inflammation in pioglitazone treated patients¹¹⁴. An additional pilot study administered pioglitazone to 29 non-diabetic patients with Alzheimer’s disease at a dose up to 45mg daily for 18 months. No adverse events leading to treatment discontinuation were seen in this trial. Peripheral edema was the principal side effect noted in pioglitazone treated subjects, but this side effect was not severe enough to lead to medication discontinuation¹¹⁵.

Common adverse events from clinical trials that occurred more frequently than placebo include upper respiratory tract infections, edema, headache, sinusitis, myalgia, and pharyngitis.

Hypoglycemia: Patients treated with insulin or other antidiabetic medication in addition to pioglitazone may be at increased risk of hypoglycemia. Due to this risk subjects with diabetes will be excluded.

The most significant potential side effect of pioglitazone is exacerbation of congestive heart failure. Due to this potential side effect, all subjects will be carefully screened for congestive heart failure (CHF) using Framingham criteria and no subjects with CHF will be enrolled, and weight will be monitored closely for increased fluid retention. Also, EKGs will be repeated every two weeks to monitor for changes.

Hepatic effects: Although there was no evidence of drug induced hepatotoxicity from clinical trials, post-marketing reports of fatal and non-fatal hepatic failure have been made in patients taking pioglitazone for diabetes. Due to this risk, liver function tests will be performed every two weeks during the trial.

Urinary Bladder Tumors: Tumors were observed in the urinary bladder of male rats in a two-year carcinogenicity study (<https://general.takedapharm.com/actoplusmetpi/>). In clinical studies, two 3-year trials in which pioglitazone was compared to placebo or glyburide, according the prescribing information “there were 16/3656 (0.44%) reports of bladder cancer in patients taking ACTOS compared to 5/3679 (0.14%) in patients not taking ACTOS. After excluding patients in whom exposure to study drug was less than one year at the time of diagnosis of bladder cancer, there were six (0.16%) cases on ACTOS and two (0.05%) cases on placebo. There are too few events of bladder cancer to establish causality.”

Fractures: In female patients with diabetes treated for a year with pioglitazone there was a higher rate of bone fractures (5.1%) compared to placebo (2.5%). There was no increase in fractures in male patients.

Laboratory Values: Clinical trials showed a slight reduction in hemoglobin and hematocrit (2-4%) over 12 weeks of treatment, likely related to increased plasma volume and not associated with any clinically significant hematologic effects.

Ovulation: Pioglitazone can increase ovulation in non-postmenopausal women. In addition, other medications in this same class have reduced the plasma concentrations of oral contraceptives. Because of these facts, female subjects must agree to an effective barrier method of contraception.

Pregnancy: Pioglitazone is pregnancy Category C. There are no known adverse events of pioglitazone during pregnancy but there are inadequate studies in humans. Animal studies using doses 10 to 40 times the maximum recommended human dose showed increased rates of post-implantation loss, delayed development, reduced fetal weights, and delayed parturition. Due to these issues all female subjects must agree to an effective barrier method of contraception.

Safety data from our pilot trial suggest a highly favorable risk/benefit profile for pioglitazone. Thirty men and women with CUD received randomly assigned treatment of pioglitazone (n=15) or placebo (n=15) in double-blind fashion for 12 weeks. Safety and tolerability were assessed via a weekly side effects questionnaire composed of 38 common symptoms, along with nurse evaluation of any adverse or serious adverse events. **The most frequent side effects reported by at least 10% of participants included not sleeping well, diarrhea, stomach pain, cough, and increased urination.** All were rated mild with none occurring significantly more frequently in the pioglitazone group. One participant in the placebo group experienced a serious adverse event (coronary artery vasospasm) that was diagnosed as cocaine-induced and required an emergency department visit.

Blood draw: The principal risk is hematoma at the venipuncture site, which is not serious and disappears after several days. CNRA phlebotomists drawing blood will be trained in venipuncture techniques to minimize extravasation.

Stress Reactivity: Cold pressor task. Individuals with cardiovascular disorders and neurological disorders should not participate in the cold-pressor task due to cardiovascular change induced by the testing. This information will be obtained during medical screening. Due to individual variation in pain and cold sensitivity, for some subjects the cold water may become too painful to sustain immersion for 120 seconds. There are no lasting effects from placing the hand and wrist in ice water (~0° Celsius) for 120 seconds.

Psychological. Items on certain questionnaires and interviews might be perceived as psychologically discomforting to some subjects. While subjects may be uncomfortable reporting these issues, the risks of serious sequelae are extremely low.

Alternative Treatments. Participants seeking treatment will be referred to appropriate treatment options.

E.2. Adequacy of Protection against Risks

E.2.1. Recruitment and Informed Consent

Participants will be self-referred in response to various study advertisements via newspaper and radio. Individuals who call for information will be given a brief description of the study. Those interested will then be asked to answer questions about their current substance use. A trained research assistant will conduct this telephone-screening interview. Eligible subjects will be scheduled for an in-person intake visit at which time a research staff member will present the informed consent form. The consent form will detail the requirements of study participation (e.g., # of visits, type of data collected, time commitment, etc.).

Subjects will be told that the purpose of the study is to evaluate a medication's effect on their alcohol use in their natural environment and following exposure to an acute stressor. Information about each study procedure will be explained. Subjects will be informed that they will attend weekly clinic sessions and to take their medication. Other information on the consent form will include a full description of study requirements, reimbursement, risks, benefits, alternatives, and the role of the local IRB. All questions will be answered before written consent is requested.

E.2.2. Protection Against Risk

Thorough screening of all subjects including history and physical examination, serum chemistry and hematology, EKG, urinalysis and Urine Drug Screen as well as structured psychiatric interviews will be completed on all subjects. Exclusion criteria include subjects at greatest risk of side effects of pioglitazone, including those with congestive heart failure, significant liver disease, edema, and diabetes, as well as risks of alcohol use (pregnant women). Monitoring of weight to capture potential fluid retention will occur at each visit. Weekly assessment for edema and urine pregnancy will occur. Twice monthly serum chemistry and hematology will take place to monitor liver functions and hemoglobin/hematocrit. In addition twice monthly EKGs will be done. Female subjects must agree to use an effective barrier method of birth control to minimize risk of pregnancy.

Confidentiality will be protected in several ways. All information collected solely for research purpose will be kept in locked, restricted access files. Subject records will be coded and filed by a number code. Subject identities will not be revealed in any publication of the data. Individual subject information will be transferred to outside sources only with the express written request of the subject. Subjects will receive a copy of their signed consent form.

E.3. Potential Benefits of the Proposed Research to the Subject and Others

There are no potential benefits for participants. However, knowledge gained from the current proposal may benefit future individuals with AUD.

E.4. Importance of the Knowledge to be Gained

Results from the current proposal may help develop novel pharmacotherapies for AUD based on mechanisms targeting PPAR. AUD is a public health issue with substantially negative effects on health and society. Results from the current proposal will help inform future medication development efforts.

The above stated risks are relatively mild in degree and procedures have been designed to minimize their probability. We believe this protocol has an extremely favorable risk/benefit ratio. The clinical research at the CNRA has an excellent track record in conducting controlled trials with the utmost attention to safety.

DATA SAFETY MONITORING PLAN

This plan describes the general data and safety monitoring procedures for the proposed study. A detailed DSM plan will be submitted for approval prior to starting the study.

1. The Principal Investigators ([name], [name]) will be responsible for knowing the policies of the local IRB. In this capacity, they will maintain accurate documentation of IRB correspondence and reports and oversee the handling of all possible study-related adverse events. The CNRA has longstanding data collection and safety monitoring system in place that will be available for the proposed study. This includes staff training, manual driven processes, weekly audit of data collection/entry, medical screening with results reviewed by on-site nurse and physician, use of standardized assessments, continued medical monitoring during treatment, use of a certified (CLIA) analytical laboratory to perform urine toxicology testing, procedures to monitor medication compliance (e.g., riboflavin), collaboration with the statistician who oversees data analysis and system management. The PI will assure that the above systems are in place and functioning properly for the duration of the study.

2. A DSM Board will be formed to provide additional, independent oversight of data related to patient safety. Membership will include Drs. [name] (UT-MDA Cancer Center), [name] (Baylor College of Medicine-Psychiatry), [name] (Baylor College of Medicine), and [name] (UTHealth). Selected individuals have relevant expertise and experience in monitoring clinical trials. This committee will perform the following activities: (a) review the research protocol and plans for data and safety monitoring; (b) evaluate study progress, including data quality, participant recruitment rates, retention rates, outcome and adverse experience data, and risk versus benefit profile; (c) make recommendations to terminate the trial because of safety concerns; and (d) protect the confidentiality of the trial.

3. Adverse events (AE) will be reported to the local IRB on an annual basis. Serious adverse events will be reported immediately (verbally within 24 hours) to the IRB, the DSMB, and to the NIDA. A written report will follow as soon as possible but in no more than three days. The written report will be in the format required by the IRB and will contain information regarding the date of the AE, description of the AE, severity rating (Grade 1 to 4), assessment of cause, whether the AE indicates an increased risk for current or future subjects, and whether changes to the informed consent form are necessary.

CITATIONS

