Figure 1. Changes in stress reactivity (left panel) and weekly measures of stress/anxiety, alcohol craving, depressive symptoms, and alcohol consumption (right panel).

Overall Study Design. To accomplish the project aims, we will utilize a double-blind, mixed-model design with a between-groups factor of dose (pioglitazone vs. placebo) and a within-subjects factor of time. We will utilize urn-randomization based on gender and severity of alcohol use (AUDIT). A summary of the study timeline, procedures, and assessments is shown in **Table 1** below.

Table 1. Outline of Study Timeline, Procedures, and Assessments

Study Week	0	1	2	3	4	5	6	7	8
Procedures and Assessments	IRB	NU	BE						
Consent and Baseline Screening	IRB	APP	OVAL						

SCID, ASI, KMSK, TLFB, CIWAA, AUDIT	X								
Receive Study Medication (Pioglitazone or Placebo)	X	X	X	X	X	X	X	X	X
Assess Medication Compliance and Adverse Events		X	X	X	X	X	X	X	X
Brief Counseling	X	X	X	X	X	X	X	X	X
Human Laboratory Assessments (Specific Aim 1)									
Stress-Reactivity Assessment (Salivary Cortisol, HR, BP, self-report)	X				X				X
Alcohol craving (self-report, brief alcohol demand)	X				X				X
Weekly Assessments (Specific Aim 2)									
Alcohol Use and Craving (TLFB, BrAC, ETG, PACS, DMQ-R)	X	X	X	X	X	X	X	X	X
Stress and Anxiety (HAM-A, PSS, PCL-5)	X	X	X	X	X	X	X	X	X
Delay Discounting, Alcohol Demand (purchasing task)	X				X		X	X	X

SCID - Structured Clinical Interview for DSM-5, **ASI** - Addiction Severity Index⁶⁵; **KMSK** - Kreek-McHugh-Schluger-Kellogg scale⁶⁶; **TLFB** - Timeline Followback⁶⁷; **CIWAA** - Clinical Institute Withdrawal Assessment for Alcohol⁶⁸; **AUDIT** – Alcohol Use Identification Test⁶⁹; **BrAC** – Breath Alcohol Concentration; **ETG** – Ethyl Glucuronide; **PACS** – Pennsylvania Alcohol Craving Scale⁷⁰; **DMQ-R** – Drinking Motives Questionnaire Revised^{1,2}. **HR** – Heart Rate; **BP** – Blood Pressure; **HAM-A** – Hamilton Anxiety Rating Scale⁷¹; **PSS** – Perceived Stress Scale⁷²; **PCL-5** - PTSD Checklist for DSM-5⁷³.

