Brief Counseling. At baseline, all participants will receive the NIAAA booklet "Rethinking Drinking: Alcohol and Your Health" providing research-based information related to alcohol use (RethinkingDrinking.niaaa.nih.gov). Study therapists will go over the booklet with the participant at the initial visit and at subsequent weekly visits using motivational interviewing techniques. At each visit, participants will also be assessed for recent alcohol use (self-report, ETG, BrAC), alcohol craving (PACS), and stress/anxiety (HAM-A, PSS). At the end of the study, referrals to local alcohol treatment services will be provided as needed.

Participant Payment & Compensation. Participants will receive \$50 for completing the baseline screening, \$25/visit for attending study visits (9 visits), \$25/assessment for completing stress reactivity

Table 2. Time Course for Assessing Stress-Induced Relapse Risk

Time (pm)	Study Procedures
3:00	Assess Craving, BAAD, Stress, Cortisol, HR, BP
3:15	Cold Pressor Task
3:20	Assess Craving, BAAD, Stress, HR, BP
3:45	Assess Craving, BAAD, Stress, Cortisol, HR, BP

assessments (3 assessments), \$10/week for medication compliance (8 weeks), and \$100 for completing the study (\$530 total). Participants will also receive \$5 compensation for busfare/parking at each study visit.

DATA ANALYTIC STRATEGY

Descriptive Statistics & Confounding Variables Descriptive statistics will evaluate measures of central tendency (continuous) and frequencies (categorical) for study-related variables. General variable relationships will be evaluated using correlation analyses. Preliminary analyses will inspect relationships between sample characteristics (e.g., demographics), predictor variables (e.g., inflammatory markers), and specified outcome variables (e.g., resilience measures) via traditional statistical tests (e.g., chi-square, Mann-Whitney-Wilcoxon, Kruskal-Wallis, and *t*-tests). Sample characteristic variables demonstrating a relationship with both the predictor and outcome variables in a given model will meet criteria as a potential confounder^{104,105} and included as a covariate in such models for hypothesis testing and explored as potential moderators of treatment group effects on experimental outcomes.

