Missingness & Multiple Comparisons Missing data will be addressed via maximum likelihood, explicit modeling of missingness, and/or imputation where appropriate. Each approach is robust to ignorable missingness (i.e. MCAR and MAR). Sensitivity analyses will permit evaluation of the robustness of findings to missing data assumptions. While Bayesian analyses are not influenced by traditional concerns of multiplicity, for the frequentist analyses, all primary outcome variables (those specified by name in the hypothesis statements below) will be evaluated at the $\alpha = 0.05$ statistical significance level. Secondary analyses will examine additional predictor and outcome variables (e.g., other inflammatory markers collected by assays); these and any otherwise *post hoc* analyses will employ false discovery rate (FDR) to control for Type I error.

Specific Analyses

Specific Aim 1: To examine the effects of pioglitazone on stress-induced relapse risk in a laboratory model. **Hypothesis 1a:** Participants receiving pioglitazone will show decreased stress reactivity (heart rate, blood pressure, salivary cortisol) compared to those receiving placebo. **Hypothesis 1b:** Participants receiving pioglitazone will show decreased alcohol craving (subjective, alcohol demand) compared to those receiving placebo.

For hypothesis 1a, GLMM will model each stress reactivity outcomes (primary: heart rate, blood pressure, and salivary cortisol) as a function of the main effects and higher-order interactions between time (baseline to Week 8), treatment (pioglitazone vs. placebo), and CPT measurement point (pre-CPT vs. post-CPT).

Follow-up analyses will examine lower-order interactions longitudinally as well as cross-sectional changes from pre- to post-CPT at each time point. Variable relationships and analyses for hypothesis 1b will follow the patterns stated above for Hypothesis 1a, with craving in place of stress reactivity.

Specific Aim 2: To examine the effects of pioglitazone on drinking, stress/anxiety, and alcohol craving in the natural environment. **Hypothesis 2a:** Participants receiving pioglitazone will show greater reductions in weekly psychometric measures of stress/anxiety measures: PSS and

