HAM-A) compared to those receiving placebo. **Hypothesis 2b:** Participants receiving pioglitazone will show greater reductions in weekly psychometric measures of alcohol craving (primary measures: PACS) compared to those receiving placebo. **Hypothesis 2c:** Participants receiving pioglitazone will show greater reductions in past week alcohol use (primary measures: heavy drinking days as defined by >3 drinks/occasion for women and >4 drinks/occasion for men, average drinks/day) compared to those receiving placebo.

For all hypotheses, GLMM will model primary outcome measures as a function of the main effects and interaction between treatment and time.

Sample Size and Power Considerations

Frequentist Analyses. Power for **Specific Aim 1** is based on the rate at which we may detect the three-way interaction between time, treatment, and CPT measurement point for a given measure of stress reactivity (transformed for normality) across $k = 1000$ Monte Carlo simulations (executed via SAS 9.4). Calculations assume the following conditions: $\alpha = 0.05$, an autocorrelation of $r = 0.50$ between consecutive observations (with a decay of $r = -0.10$ for subsequent observations), and a small correlation of $r = 0.05$ for observations occurring at the same time point across groups. Based on these assumptions, the different sample sizes (pragmatic and pessimistic) stipulated in **Table 3** each provide power to detect small-to-moderate effect sizes (treatment group differences expressed as Cohen's D, with effects unfolding in linear fashion over time). Power for **Specific Aim 2** is based on evaluating reductions in drinks per week. Estimates are derived using G*Power 3.1.9.2. Assuming $\alpha = 0.05$ (two-tailed) and an average baseline of drinks/week across participants (calculated as an average from 14 and 7 drinks/week for a 3:1 ratio of males to females, respectively), the different sample sizes (pragmatic and pessimistic) stipulated in **Table 3** each provide power to detect varying decreases in alcohol consumption.

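### Gender and AUDIT steer the urn randomisation but are in no primary model, and the covariate rule will rarely admit them; power is lost only where they predict change over time

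*Combined protocol and SAP*

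**What the plan says.** **Randomisation.** Under Approach, Overall Study Design: "We will utilize urn-randomization based on gender and severity of alcohol use (AUDIT"). The AUDIT cut-point and the urn parameters are not given. Table 1 shows AUDIT collected at Week 0.

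**Aim 1 model.** Under Specific Analyses, each stress-reactivity outcome is modelled "as a function of the main effects and higher-order interactions between time (baseline to Week 8), treatment (pioglitazone vs. placebo), and CPT measurement point". Craving (Hypothesis 1b) follows the same pattern. Power is based on "the rate at which we may detect the three-way interaction between time, treatment, and CPT measurement point".

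**Aim 2 model.** "For all hypotheses, GLMM will model primary outcome measures as a function of the main effects and interaction between treatment and time". Neither aim's model names gender or AUDIT.

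**Covariate rule.** Under Descriptive Statistics & Confounding Variables, the candidates are "Sample characteristic variables demonstrating a relationship with both the predictor and outcome variables in a given model". Those that qualify become covariates in the hypothesis tests and are explored as moderators. No threshold is given, and the randomisation factors are not mentioned.

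**The concern.** When randomisation is balanced on prognostic factors, the usual course is to carry those factors into the analysis. Otherwise the variation they explain stays in the error term although the allocation has already evened it out between arms. The standard error is then larger than it need be, and the test rejects a true null less often than its nominal 5%.

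Here the omission is compounded by the covariate rule. It asks for an association with treatment, which is what the urn is designed to prevent. The better the urn works, the less likely the rule is to admit gender or AUDIT. Any factor it does admit is chosen after looking at the imbalance, against no stated criterion.

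At stake are a few points of power in a trial of 50 completers. Table 3 shows only 71.8% (Aim 1) and 74.6% (Aim 2) for the smallest effects at N = 40.

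**Working it through.** **Inputs.**
- From the documents: N = 50 completers, 25 per group (Participants; Table 3). The Human Subjects section gives other enrolment figures; 50 is used because Table 3 uses it. Male to female ratio 3:1, so 25% women. Two-sided alpha 0.05. Visits at Weeks 0-8 for Aim 2; three visits with pre- and post-CPT values for Aim 1.
- Assumed: the share R² of the variance in change explained by gender and AUDIT together (0-30%); AUDIT split at its median for the urn; a standard urn that starts with one ball per arm in each gender-by-AUDIT cell and adds one of the opposite arm after each assignment; a standardised effect d = 0.8, chosen so that unadjusted power is about 80%.

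**The plan's own power figures.** Table 3 does not reproduce from its printed inputs. For Aim 1 at N = 50 and D = 0.50/0.40/0.30, a simple two-mean test gives 42/29/18%, against the stated 100.0/97.8/84.6%. For Aim 2 the test family, exposure and dispersion are not stated. This shows missing inputs, not a proven error, and the present point does not rest on Table 3.

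**Step 1: how often the rule would admit the factors.** Taking p < 0.05 against arm as the criterion, simulation under the urn flags gender in about 0.3% of trials and AUDIT in 1-2%. Simple randomisation would flag each in about 5%.

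**Step 2: which test is affected.** With complete visits, treatment-by-time is estimated from within-person contrasts, and a stable difference in level cancels. In Gaussian mixed models (50 people, 9 visits), adding gender and AUDIT as main effects left the estimate unchanged. The standard error was 0.2119 with and without them under a random intercept, and 0.247 both ways under a random slope, even where they explained 30% of the between-person variance in level. Only interactions of the factors with time alter the tested contrast. Some random-slope fits gave convergence warnings.

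**Step 3: size if the factors predict change.** With exact balance, the unadjusted statistic has null variance 1 − R², so

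size = 2[1 − Φ(1.96/√(1 − R²))].

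For R² = 0.10: 1.96/0.949 = 2.07, size 3.9%. For R² = 0.30: 1.96/0.837 = 2.34, size 1.9%. These are limiting values. The urn balances imperfectly and sees AUDIT only as high or low, so the simulated size lies closer to 5%.

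**Step 4: power with adjustment.** In large samples,

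power = Φ(d√(N/4)/√(1 − R²) − 1.96), with d√(N/4) = 0.8 × √12.5 = 2.83.

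For R² = 0: Φ(0.87) = 81%. For R² = 0.10: Φ(2.98 − 1.96) = 85%. For R² = 0.30: Φ(3.38 − 1.96) = 92%. The simulated values are slightly lower because of the t distribution, the degrees of freedom spent and residual imbalance.

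**Simulated results** (two-group test on change, repeated runs):

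| R² of change (assumed) | Unadjusted size | Gain in power from about 80% |
|---|---|---|
| 0% | about 5% | about −1 point |
| 5% | about 4.4% | about +1 |
| 10% | 4-4.5% | +2 to +3 |
| 20% | about 4% | +6 to +7 |
| 30% | 3.2-3.5% | +8 to +10 |

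With 4,000 runs the Monte Carlo standard error of a 5% size is √(0.05 × 0.95/4000) = 0.34 points, so the 5% row is not clearly below nominal.

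**Step 5: where a link with change is plausible.** The power section takes 14 drinks/week for men and 7 for women, and Table 3 states the Aim 2 effect as a percentage fall. A common 12% fall is 0.12 × 14 = 1.68 drinks/week for men and 0.12 × 7 = 0.84 for women. If average drinks/day is analysed as continuous with the identity link described under Statistical Modeling, gender then predicts absolute change. Assuming a between-person coefficient of variation of 0.4-0.8 and a mean reduction of 30-80%, simulation puts gender's share alone at about 4-21%. On a log link the equal percentage falls cancel.

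**The case against.** The strongest reply is that the harm is hypothetical. The hypotheses concern reductions over time, and the evidence tying gender and AUDIT to drinking concerns level. The entry limits show that men and women may start at different levels. The gender-specific heavy-day cut-offs only adjust the definition, and say nothing about change. For heart rate, blood pressure, cortisol, PSS, HAM-A and PACS, no link with either factor is documented. Below about 5% of variance explained, adjustment is neutral or slightly harmful. All of this stands, and it is why the loss must be stated as conditional.

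A reader might also infer that the rule can never admit gender or AUDIT. The documents do not support that. An urn leaves some imbalance, AUDIT can differ between arms within its category, attrition from 60 to 50 can add more, and no threshold is set. Reading the rule's predictor as treatment is itself an inference, since the section's own example of a predictor is inflammatory markers, though treatment is the predictor of interest in the primary models.

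The reply does not remove the omission. Two factors important enough to steer allocation are left to a screen that works against them.

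**Conclusion.** The omission is certain; its consequence is not. Gender and AUDIT steer the randomisation, appear in no primary model, and will rarely pass the covariate rule. Where they predict change over time, or change in the CPT response, the treatment-by-time test is somewhat conservative and loses power by the amounts tabulated above. This is most plausible for average drinks/day on the identity scale.

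A reader might go further and infer that every primary test has lost precision and runs below 5%. That does not follow: stable differences cancel in the tested interaction, and no section states an association with change. Nor is there any inflation of false positives.

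The sizes rest on the assumed R², urn, AUDIT split and d = 0.8, and on a Gaussian test of change. Poisson and binomial mixed models were not simulated. This is a cheap improvement, not a flaw that threatens the trial's conclusions.

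**What to change.** Add to Specific Analyses, for the frequentist and Bayesian models alike: *All Aim 1 and Aim 2 primary models will include gender and continuous baseline AUDIT, each with its interaction with linear time and, in Aim 1, with CPT point and time by CPT point, regardless of observed balance.* State that the association-with-treatment test does not apply to these two variables, and give the AUDIT cut-point used by the urn. The interactions are needed because main effects alone leave the treatment-by-time test unchanged in a Gaussian mixed model with complete visits.

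**Cost.** No new data. With linear time for the covariates, Aim 2 gains 2 × (1 main + 1 time) = 4 parameters and Aim 1 gains 2 × (1 main + 1 time + 1 CPT + 1 time-by-CPT) = 8. With categorical time the counts are 2 × 9 visits = 18 and 2 × (3 visits × 2 CPT points) = 12, heavy for 50 people. About 1 point of power is lost if the factors do not predict change. For any logit-link outcome the treatment effect becomes conditional on the covariates, and the SAP should say so.
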